3. OBJECTIVES AND ENDPOINTS

The objectives which will be evaluated in this study and endpoints associated with each objective are provided in [Table 2](#).

Table 2: Study Objectives and Endpoints

Objectives	Endpoints
Primary	

 To evaluate the humoral immunogenicity of mRNA-1010 relative to that of an active comparator against vaccine-matched influenza A and B strains at Day 29 	
 GMT at Day 29 as measured by HAI assay Proportion of participants reaching seroconversion at Day 29 as measured by HAI assay

 To evaluate the safety and reactogenicity of mRNA-1010 	
 Frequency and grade of each solicited local and systemic reactogenicity AR during a 7-day follow-up period post vaccination Frequency and severity of any unsolicited AEs during the 28-day follow-up period post vaccination Frequency of any SAEs, AESIs, MAAEs, and AEs leading to discontinuation from Day 1 through Day 361 (Month 12)/EoS
Secondary	

 To further evaluate the immunological response of mRNA-1010 (for superiority) relative to an active comparator against vaccine-matched influenza A virus strains at Day 29 	
 GMT at Day 29 as measured by HAI assay Proportion of participants reaching seroconversion at Day 29 as measured by HAI assay

 To evaluate relative vaccine efficacy to prevent influenza caused by any strain of influenza virus 	
 First episode of RT-PCR–confirmed protocol-defined ILI that begins at least 14 days postvaccination through Day 181 (Month 6)/end of influenza season caused by any strain of influenza virus regardless of antigenic match to the strains selected for the seasonal vaccine First episode of RT-PCR–confirmed Centers for Disease Control and Prevention (CDC)–defined ILI that begins at least 14 days postvaccination through Day 181 (Month 6)/end of influenza season caused by any strain of influenza virus regardless of

Objectives	Endpoints

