7. DELAY OR DISCONTINUATION OF STUDY INTERVENTION AND PARTICIPANT DISCONTINUATION/WITHDRAWAL

7.1 Participant Discontinuation/Withdrawal From the Study

Participants who withdraw or are withdrawn from the study will not be replaced.

From an analysis perspective, a “withdrawal” from the study refers to a situation wherein a participant does not return for the final visit planned in the protocol.

Participants can withdraw consent and withdraw from the study at any time, for any reason, without prejudice to further treatment the participant may need to receive. The investigator will request that the participant complete all study procedures pending at the time of withdrawal.

If a participant desires to withdraw from the study because of an AE, the investigator will attempt to obtain agreement to follow-up with the participant until the event is considered resolved or stable and will then complete the EoS section of the eCRF.

All data collected until the date of withdrawal or last contact of the participant will be used for the analysis.

Information related to the withdrawal will be documented in the eCRF. The investigator will document whether the decision to withdraw a participant from the study was made by the participant or by the investigator, as well as which of the following possible reasons was responsible for withdrawal:

- AE (specify)
- SAE (specify)
- Solicited AR or reactogenicity event (specify)
- Death
- Lost to follow-up (LTFU)
- Physician decision (specify)
- Pregnancy
- Protocol deviation
- Study terminated by Sponsor
- Withdrawal of consent by participant (specify)
- Other (specify)

Participants who are withdrawn from the study because of AEs (including SAEs, solicited ARs, or reactogenicity events) must be clearly distinguished from participants who are withdrawn for other reasons. Investigators will follow-up with participants who are withdrawn from the study as result of an AE, SAE, solicited AR, or reactogenicity event until resolution of the event.

A participant withdrawing from the study may request destruction of any samples taken and not tested, and the investigator must document this in the site study records.

If the participant withdraws consent for disclosure of future information, the Sponsor may retain and continue to use any data collected before such a withdrawal of consent (see [Section 11.1.6](#)).

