9.5.3 Safety Analyses

All safety analyses will be based on the Safety Set, except summaries of solicited ARs, which will be based on the Solicited Safety Set. All safety analyses will be provided by vaccination group. Participants will be included in the vaccination group corresponding to what they actually received.

Safety and reactogenicity will be assessed by clinical review of all relevant parameters, including solicited ARs (local and systemic events), unsolicited AEs, SAEs, AESIs, MAAEs, and AEs leading to discontinuation.

The number and percentage of participants with any solicited local AR, solicited systemic AR, and solicited AR during the 7-day follow-up period after the injection will be summarized. A 2-sided 95% exact CI using the Clopper-Pearson method will also be provided for the percentage of participants with any solicited AR.

The number and percentage of participants with unsolicited AEs, treatment-related AEs, severe AEs, SAEs, MAAEs, AESIs, and AEs leading to withdrawal from study participation will be summarized. Unsolicited AEs will be coded according to the MedDRA and presented by MedDRA system organ class and preferred term.

Solicited ARs will be coded by system organ class and preferred term according to the MedDRA for AR terminology. The Toxicity Grading Scale for Healthy Adult and Adolescent Volunteers Enrolled in Preventive Vaccine Clinical Trials (DHHS 2007b) will be used in this study with modification for rash, solicited ARs, and vital signs.

The number of events of unsolicited AEs, SAEs, AESIs, and MAAEs will be reported in summarization tables accordingly.

Table 8 summarizes the analysis strategy for safety parameters. For all other safety parameters, descriptive summary statistics will be provided. Further details will be described in the SAP.

Table 8: Analysis Strategy for Safety Parameters

Safety Endpoint	Number and Percentage of Participants, Number of Events	95% CI
Any solicited AR (overall and by local, systemic)	X	X
Any unsolicited AE	X	–
Any SAE	X	–
Any unsolicited MAAE	X	–
Any unsolicited AESI	X	–
Any unsolicited treatment-related AE	X	–
Any treatment-related SAE	X	–
Any unsolicited AE leading to withdrawal from study participation	X	–
Any severe unsolicited AE	X	–
Any treatment-related severe unsolicited AE	X	–

Abbreviations: AE = adverse event; AESI = adverse event of special interest; AR = adverse reaction; CI = confidence interval; MAAE = medically attended adverse event; SAE = serious adverse event.

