3.1 Primary Endpoints

The **co-primary immunogenicity endpoints** are:

- Geometric mean titer (GMT) of anti-hemagglutinin (HA) antibodies as measured by hemagglutination inhibition (HAI) against vaccine-matched influenza A and B strains at Day 29

- Proportion of participants reaching seroconversion at Day 29 against vaccine-matched influenza A and B strains as measured by HAI

The GMT as measured by an assay will be calculated using the following formula:

$$\text{GMT} = 2^{\left\{ \frac{\sum_{i=1}^n \log_2(t_i)}{n} \right\}}$$

where, for n participants, t_i is the immunogenicity titer measurement for participant i .

Rate of seroconversion is defined as the proportion of participants with either a pre-vaccination HAI titer $< 1:10$ and a post-vaccination titer $\geq 1:40$ or a pre-vaccination HAI titer $\geq 1:10$ and a minimum 4-fold rise in post-vaccination HAI antibody titer.

The **primary safety endpoints** are:

- Frequency and grade of each solicited local and systemic reactogenicity adverse reaction (AR) during a 7-day follow-up period post-vaccination
- Frequency and severity of any unsolicited adverse events (AE) during the 28-day follow-up period post-vaccination
- Frequency of any serious adverse events (SAE), adverse events of special interests (AESI), and medically attended adverse events (MAAE) and AEs leading to discontinuation from Day 1 through Day 361 (Month 12)/ End of Study (EoS).

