6.6.1 Analysis of Solicited Adverse Reactions

An AR is defined as any AE for which there is a reasonable possibility that the IP may have caused the AE. The term “Solicited Adverse Reaction” refers to selected signs and symptoms occurring after IP injection during a specified post-injection follow-up period (day of injection and 6 subsequent days).

The solicited ARs are recorded by the participant in the eDiary. The eDiary will solicit daily participant reporting of occurrence and intensity of ARs using a structured checklist from Day 1 through 7 days after the IP injection (i.e., the day of injection and 6 subsequent days). Any solicited ARs started during the 7-day follow-up period post-injection, if not reported in the eDiary, should be entered on the Reactogenicity eCRF and will be included in the evaluation of solicited ARs in addition to the eDiary.

If a solicited local or systemic AR starts on or after Day 8, it should be captured on the AE eCRF page until no longer reported.

Any solicited AR that meets any of the following criteria must be entered into the participant’s source document and must be recorded in the participant’s Reactogenicity eCRF:

- Solicited local or systemic AR that results in a visit to a healthcare practitioner
- Solicited local or systemic AR leading to the participant withdrawing from the study or the participant being withdrawn from the study by the investigator (AE leading to withdrawal)
- Solicited local or systemic AR continuing beyond 7 days post-injection
- Solicited local or systemic AR that otherwise meets the definition of an SAE

The following local ARs will be solicited by the eDiary: injection site pain, injection site erythema (redness), injection site swelling/induration (hardness), and axillary swelling or tenderness ipsilateral to the side of injection.

The following systemic ARs will be solicited by the eDiary: headache, fatigue, myalgia, arthralgia, nausea/vomiting, chills, and fever (oral).

The solicited ARs will be graded based on the grading scales presented in the protocol, modified from the Toxicity Grading Scale for Healthy Adult and Adolescent Volunteers Enrolled in Preventative Vaccine Clinical Trials (DHHS 2007b) in [Section 9.6](#). Grading of Grade 4 events will be determined per investigator and assessment is recorded on the reactogenicity event page in the eCRF .

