6.6.2.1 Overview of Unsolicited TEAEs

An overall summary of unsolicited TEAEs up to 28 days after IP injection (or other time frames, as applicable) including the number and percentage of participants who experienced the following will be presented:

- Any unsolicited TEAEs
- Any unsolicited treatment-related TEAEs
- Any serious TEAEs
- Any treatment-related serious TEAEs
- Any unsolicited severe TEAEs
- Any unsolicited treatment-related severe TEAEs
- Any unsolicited medically attended TEAEs
- Any unsolicited treatment-related medically attended TEAEs
- Any unsolicited treatment emergent AESI
- Any unsolicited TEAEs leading to discontinuation from participation in the study.

Listings containing individual participant AE data for unsolicited AEs, unsolicited AEs leading to discontinuation from participation in the study, SAEs, AESI, MAAEs will be provided separately.

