6.6.2.2 TEAEs by System Organ Class and Preferred Term

The following summary tables of TEAEs up to 28 days after IP injection will be provided by SOC and PT using frequency counts and percentages (i.e., number and percentage of participants with an event) and number of events:

- Any unsolicited TEAEs

- Any unsolicited treatment-related TEAEs
- Any serious TEAEs
- Any treatment-related serious TEAEs
- Any unsolicited severe TEAEs
- Any unsolicited treatment-related severe TEAEs
- Any unsolicited medically attended TEAEs
- Any unsolicited treatment-related medically attended TEAEs
- Any unsolicited treatment emergent AESI
- Any unsolicited TEAEs leading to discontinuation from participation in the study.

Unsolicited TEAEs and unsolicited treatment related TEAEs will be summarized by SOC and PT for TEAEs with occurrence in $\geq 1\%$ of participants in any vaccination group based on PT and also presented by SOC and PT and severity using frequency counts and percentages.

Summary tables for all unsolicited SAEs, AESIs, MAAEs, AE leading to discontinuation from the study, and TEAE leading to death up to 180 days after vaccine, and through Day 361 (Month 12)/EoS will be provided also be provided by SOC and PT as applicable.

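### The MAAE and discontinuation tables are limited to unsolicited events, although the primary safety endpoint counts any such event and the plan classes some solicited reactions as such events

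*SAP*

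**What the plan says.** The endpoint is unrestricted. Protocol Table 2 gives it as "Frequency of any SAEs, AESIs, MAAEs, and AEs leading to discontinuation from Day 1 through Day 361 (Month 12)/EoS", and SAP 3.1 says the same.

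Solicited reactions can belong to it. Protocol 8.11.3 lists solicited reactions that need an entry on the Reactogenicity eCRF page. One that results in a visit to a healthcare practitioner is labelled there as an MAAE, and one that leads to withdrawal as an AE leading to withdrawal. SAP 6.6.1 repeats the list, including "Solicited local or systemic AR leading to the participant withdrawing from the study", and keeps the withdrawal label. Protocol 7.1 gives a solicited reaction its own category among the reasons for withdrawal and treats such a withdrawal as one due to an AE.

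The tables are narrower. Protocol Table 8 has a row for "Any unsolicited AE leading to withdrawal from study participation" and words its MAAE row the same way. SAP 6.6.2.1 has "Any unsolicited TEAEs leading to discontinuation from participation in the study" and likewise limits its MAAE rows and its listing of discontinuations. SAP 6.6.2.2 repeats these rows for the 28-day tables by system organ class and preferred term. For the later tables it announces "Summary tables for all unsolicited SAEs, AESIs, MAAEs, AE leading to discontinuation from the study" up to 180 days and through Day 361.

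**The concern.** Under the row wording, a participant who saw a doctor or left the study because of, say, injection-site pain or fatigue on Day 2 meets the endpoint definition but falls outside the tables meant to report it. Solicited reactions in the first week are a plausible place for two different vaccine platforms to differ. An undercount of care-seeking and withdrawal caused by them would therefore touch a comparison the trial exists to describe. The word is hard to dismiss as a slip, because in the same lists the SAE rows omit it. A programmer would have reason to apply the distinction.

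**Working it through.** The plan states no figure on this point, so the check is mainly a comparison of text. The scope of each output is as follows.

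| Place | MAAE | AE leading to discontinuation | SAE |
|---|---|---|---|
| Endpoint: Protocol Table 2, SAP 3.1 | any | any | any |
| Protocol 9.5.3, running text | not limited | not limited | not limited |
| Protocol Table 8 | unsolicited | unsolicited | any |
| SAP 6.6.2, running text | not limited | not limited | not limited |
| SAP 6.6.2.1, overview | unsolicited | unsolicited | not limited |
| SAP 6.6.2.1, listings | not limited | unsolicited | not limited |
| SAP 6.6.2.2, 28-day tables | unsolicited | unsolicited | not limited |
| SAP 6.6.2.2, 180-day and Day 361 tables | unsolicited | unsolicited | unsolicited |

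In the last row the word heads a list. If it governs the whole list, all three columns are limited. If it governs only the first item, SAEs alone are limited. Either way it conflicts with every other SAE entry in the table.

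**Does another output fill the gap?** The solicited-reaction analyses in SAP 6.6.1 give any reaction, each reaction by grade, day of onset, duration, persistence beyond 7 days and delayed onset. None counts reactions that were medically attended or led to withdrawal. Two outputs capture part of it:

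- *Toxicity grade (Protocol Table 5, SAP Table 9).* Grade 4 for pain, axillary swelling, headache, fatigue, myalgia, arthralgia, chills and nausea/vomiting involves an emergency room visit or hospitalization. Grade 3 nausea/vomiting refers to outpatient intravenous hydration, and Grade 3 chills to medical intervention. Grade 3 fatigue, myalgia and arthralgia are defined by activity alone, and fever by temperature alone. An office visit for one of these cannot be seen from the grade.
- *Disposition (SAP 6.2.1).* Reasons for discontinuation are tabulated by vaccination group, so a withdrawal for a solicited reaction would appear there. MAAEs do not.

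**Size.** Expected number affected = n × r, with n = 3000 mRNA-1010 recipients (Protocol Table 3) and r the proportion with a solicited reaction that leads to a healthcare visit or withdrawal. The documents do not give r. Over an assumed range:

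- r = 0.05%: 3000 × 0.0005 = 1.5
- r = 0.1%: 3000 × 0.001 = 3
- r = 0.5%: 3000 × 0.005 = 15
- r = 1%: 3000 × 0.01 = 30

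For reference, the one planned safety figure is the chance of seeing at least one event at a true rate of 0.1%. It reproduces: 1 − (1 − 0.001)^3000 = 0.9503, against the stated value of about 95%. It is not in dispute.

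**The case against.** The strongest reply is that this is loose wording and not a settled exclusion. SAP 6.6.2 promises summaries of MAAEs and AEs leading to withdrawal without the limit, and so does the running text of Protocol 9.5.3. SAP 6.6.2 also says that unsolicited AEs are collected on both the AE page and the reactogenicity page. The definition of an unsolicited AE in Protocol 8.11.1 is garbled, and one clause can be read as taking in solicited reactions. This part stands: a reader might infer that these events are certain to be missing, and the documents do not establish that.

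It does not remove the conflict. The unqualified SAP text sits under a heading on unsolicited events. SAP 6.6.1 assigns solicited reactions entered on the Reactogenicity page to the solicited-reaction evaluation, and SAP 6.1 sets solicited reactions apart from the 28-day unsolicited period. The row lists are the more specific instruction.

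A reader might also infer that SAEs are lost in the same way. The documents do not support that. The overview and 28-day SAE rows and Protocol Table 8 are unrestricted, and SAP 6.1 includes SAEs in the 7-day period. A solicited reaction starts within 7 days, so a serious one with onset then belongs in the 28-day SAE rows. AESIs are not materially affected either: the categories in Protocol 11.3 do not overlap the solicited list.

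The partial capture by grade and disposition is real. It leaves less severe attended reactions without an explicit count, and it does not report the endpoint as defined.

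**Conclusion.** The MAAE and discontinuation rows in Protocol Table 8, SAP 6.6.2.1 and SAP 6.6.2.2 are wrong as written. They are narrower than the primary safety endpoint they report, and they disagree with unqualified text in the same documents. Following the row wording would undercount the endpoint. For SAEs the defect is a single inconsistent sentence in SAP 6.6.2.2.

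The size is unknown. About 1.5 to 30 of 3000 mRNA-1010 recipients follows only from the assumed range of 0.05% to 1%. A reader might infer that the safety comparison is biased towards no difference. That holds only if mRNA-1010 is the more reactogenic arm, and the documents give no comparative rates. Even then, the grade and disposition tables would show part of any excess.

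**What to change.** In Protocol Table 8, SAP 6.6.2.1 and SAP 6.6.2.2:

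- Remove *unsolicited* from the MAAE and discontinuation rows, from the listing of discontinuations, and from the sentence on the 180-day and Day 361 tables.
- Count every event that meets the definition, from both the AE and the Reactogenicity eCRF pages, and state which pages feed each table.
- Show the solicited and unsolicited components as sub-rows, so that the unsolicited counts remain visible.

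The cost is revised wording and new table shells, and counts that may look slightly less favourable. No new assessment is needed, because the documents already require these reactions to be recorded. The eCRF is not among the documents, so the sponsor should confirm that the Reactogenicity page identifies medical attendance and withdrawal in a form that can be tabulated.

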6.6.2.2 TEAEs by System Organ Class and Preferred Term

The following summary tables of TEAEs up to 28 days after IP injection will be provided by SOC and PT using frequency counts and percentages (i.e., number and percentage of participants with an event) and number of events:

- Any unsolicited TEAEs

- Any unsolicited treatment-related TEAEs
- Any serious TEAEs
- Any treatment-related serious TEAEs
- Any unsolicited severe TEAEs
- Any unsolicited treatment-related severe TEAEs
- Any unsolicited medically attended TEAEs
- Any unsolicited treatment-related medically attended TEAEs
- Any unsolicited treatment emergent AESI
- Any unsolicited TEAEs leading to discontinuation from participation in the study.

Unsolicited TEAEs and unsolicited treatment related TEAEs will be summarized by SOC and PT for TEAEs with occurrence in $\geq 1\%$ of participants in any vaccination group based on PT and also presented by SOC and PT and severity using frequency counts and percentages.

Summary tables for all unsolicited SAEs, AESIs, MAAEs, AE leading to discontinuation from the study, and TEAE leading to death up to 180 days after vaccine, and through Day 361 (Month 12)/EoS will be provided also be provided by SOC and PT as applicable.

6.6.2.3 TEAEs by Preferred Term

The following summary tables of TEAEs will be provided by PT sorting by frequency on the mRNA-1010 group:

- All unsolicited TEAEs
- SMQ

6.6.2.4 TEAEs by Severity

The following summary tables of TEAEs will be provided by the severity using frequency counts and percentages:

- All unsolicited TEAEs
- All unsolicited treatment-related TEAEs

6.6.3 Subgroup Analysis of TEAEs

Analysis of unsolicited TEAEs will be conducted for subgroups defined in [Table 5](#). Subgroup analysis for TEAE may be performed for the specified TEAE category based on [Section 6.6.2.1](#).

Overall summary of the unsolicited TEAEs up to 28 days will be provided for each subgroup. Summary tables for TEAE, treatment related TEAEs, and SAEs by SOC and PT will also be provided for each subgroup up to 28 days after the vaccine.

6.6.4 Death

Total number of deaths due to any cause and time of death from the injection (numeric and by time point window) will be summarized in a table.

6.6.5 Other Safety Data

6.6.5.1 Pregnancy

A pregnancy test via blood or point-of-care urine test will be performed for all female participants of childbearing potential at the Screening Visit and before the vaccine dose on Day 1, if Day 1 is not on the same day as the Screening Visit. At the discretion of the investigator, a pregnancy test either via blood or point-of-care urine can be performed at any time. Additional pregnancy testing during the study may also be performed at the discretion of the investigator. Pregnancy test results will be listed by participant.

6.6.5.2 Vital Signs

On the day of vaccination, vital signs measurements including systolic and diastolic blood pressures, heart rate, respiratory rate, and body temperature will be collected once before vaccination and once 30 minutes after vaccination.

Observed value and change from pre-injection (baseline) to post- injection in vital signs will be summarized by vaccination group. Abnormal vital sign measurements will be graded per toxicity grading criteria provided in [Section 9.7](#). A toxicity grade shift table of the vital signs from pre-injection to post-injection will be provided. Additionally, the values that are outside the reference ranges will be flagged in a data listing. Participant with any abnormal vital sign measurement where toxicity grade (Grade 3 or higher) will be listed separately.

